3. LIST OF ABBREVIATIONS AND DEFINITIONS OF TERMS

The following abbreviations and specialist terms are used in this study protocol.

Table 1: Abbreviations and Specialist Terms

Abbreviation or Specialist Term	Explanation
AE	Adverse event
ALT	Alanine aminotransferase
AST	Aspartate aminotransferase
AUC ₀₋₈	Area under the curve from time zero to 8 hours
AUC _{inf}	Area under the curve from time zero to infinity
BioAegis	BioAegis Therapeutics, Inc. or Sponsor
CAP	Community-acquired pneumonia
CBC	Complete blood count
CDC	Centers for Disease Control and Prevention
C _{max}	Maximum concentration
COPD	Chronic obstructive pulmonary disease
CPK	Creatinine phosphokinase
CRO	Contract Research Organization
CRP	C-reactive protein
CTCAE	Common Terminology Criteria for Adverse Events
CURB-65	C onfusion, U rea >7 mmol/L, R espiratory rate ≥30/min, B lood pressure systolic <90 or diastolic ≤60, and age ≥ 65 years
CXR	Chest x-ray
eCRF	Electronic case report form
CT	Computed tomography
DSMB	Data and Safety Monitoring Board
ED	Emergency department
EDC	Electronic data capture
EKG	Electrocardiogram
ELISA	Enzyme-linked immunosorbent assay
EOS	End of Study
f-actin	Filamentous actin
g-actin	Globular actin
GCP	Good Clinical Practice

Abbreviation or Specialist Term	Explanation
HIV	Human immunodeficiency virus
ICH	International Council for Harmonization of Technical Requirements for Pharmaceuticals for Human Use
ICU	Intensive Care Unit
IEC	Independent Ethics Committee
IRB	Institutional Review Board
IRR	Injection-related reaction
IUD	Intrauterine device
IV	Intravenous
IWRS	Interactive web response system
LDH	Lactate dehydrogenase
MAD	Multiple-ascending dose
MMSE	Mini-Mental State Examination
MTD	Maximum tolerated dose
MV	Mechanical ventilation
NCI	National Cancer Institute
NSAIDS	Non-steroidal anti-inflammatory drugs
NSS	Normal saline solution
PD	pharmacodynamic
PDF	Portable document format
PE	Physical examination
PI	Principal Investigator The investigator who leads the study conduct at an individual study site. Every study site has a principal investigator.
PK	Pharmacokinetics
PSI	Pneumonia Severity Index
rhu-pGSN	Recombinant human plasma Gelsolin
SAE	Serious adverse event
SAP	Statistical analysis plan
SD	Single dose
SOC	Standard of care
SOFA	Sequential Organ Failure Assessment
T _{1/2}	Terminal half-life

Abbreviation or Specialist Term	Explanation
Tmax	Time to maximum concentration
US	United States
VP	Vasopressor
WBC	White blood cell
WHO	World Health Organization

4. INTRODUCTION

4.1. Community-Acquired Pneumonia

Pneumonia is an inflammatory condition of the lung primarily affecting the alveoli. It is usually caused by infection with viruses or bacteria and less commonly other microorganisms. Certain drugs and other conditions such as autoimmune diseases may cause a similar clinical picture.

Typical symptoms include a cough, chest pain, fever, and difficulty breathing. Diagnostic tools include chest x-rays (CXRs), serology, microscopy of a sputum smear and culture of the sputum. Treatment depends on the underlying cause. Pneumonia documented or presumed to be viral, bacterial or fungal is treated with appropriate agents when available. If the pneumonia is severe, the affected person is admitted to hospital.

According to the World Health Organization (WHO), pneumonia due to infection affects approximately 450 million people globally per year, seven percent of the population, and results in about 4 million deaths, mostly in third-world countries; however, it remains a serious issue in the developed world, as well. In the United States (US), 1.1 million are hospitalized each year, resulting in over 52,000 deaths at a ratio of 16.8 deaths per 100,000 ([Centers for Disease Control and Prevention \[CDC\], 2010](#); [Kochanek et al, 2015](#)).

Pneumonia is classified according to the etiologic organism, and where the infection was acquired (community or hospital facility).

Community-acquired pneumonia (CAP) is the most common type of pneumonia, and may be caused by pyogenic bacteria, atypical bacteria, viruses or fungi which often cannot be identified in real time. CAP may also have non-infectious etiologies, including allergic, immune-mediated, toxins, or drugs. CAP occurs throughout the world and is a leading cause of illness and death.

The following outcome prediction models will be used in the current study:

- CURB-65: a simple five-point score in which one point is allocated to the presence of each of the following: **C**onfusion, **U**rea >7 mmol/L, **R**espiratory rate ≥ 30 /min, **B**lood pressure systolic <90 or diastolic ≤ 60 , and age ≥ 65 years ([Appendix A](#); [British Thoracic Society, 1987](#); [Neill et al, 1996](#); [Niederman et al, 2001](#); [Lim et al, 2003](#); [Richards et al, 2011](#)).
- Pneumonia Severity Index (PSI): calculates the probability of morbidity and mortality among patients with CAP ([Appendix C](#); [Richards et al, 2011](#)).
- Sequential Organ Failure Assessment (SOFA): calculates the number and the severity of organ dysfunction in six organ systems (respiratory, coagulation, liver, cardiovascular, renal, and neurologic) ([Appendix D](#)) ([Singer et al, 2016](#)).

4.2. Current Treatment of CAP

CAP antibiotic, anti-fungal or anti-viral agents are administered based on organisms present in sputum, bacteriologic culture, serum antibody results or clinical impression of the infecting organism until resolution of sepsis and clinical symptoms and radiographic improvement has occurred, typically of 5- to 14-days duration. Patients with CURB-65 score ≥ 3 have an unacceptably high mortality despite standard-of-care (SOC) therapy and should be admitted to

hospital and may need intensive care (Richards et al, 2011). Any associated organ dysfunction is supported in an intensive care unit (ICU) and may include vasopressors and fluids for shock and mechanical ventilation for respiratory failure. Oral antibiotic therapy may be continued after discharge from hospital.

4.3. Plasma Gelsolin and Treatment of CAP

Plasma gelsolin is a human protein produced and secreted by virtually every cell type, and it circulates at high levels in the blood of healthy individuals. At normal levels of 200-300 mg/L, it is the fourth most abundant protein in the circulation.

The therapeutic protein being developed by BioAegis Therapeutics, Inc. (BioAegis or Sponsor) is recombinant human plasma gelsolin (rhu-pGSN) and was formerly referred to as BG9385. It is identical to the complete natural protein and is comprised of 755 amino acids. The protein, like the natural protein, is non-glycosylated. The protein consists of six repeated domains, which make up three distinct actin binding sites, two that bind globular actin (G-actin) and one that binds filamentous actin (F-actin). Domain 1 plus the first 10 amino acids of domain 2 of gelsolin is the minimal fragment size required for its actin severing activity. Rhu-pGSN contains multiple calcium binding sites that regulate its activity. It is a highly conserved protein, as far back as *Drosophila*.

Plasma gelsolin modulates inflammation while at the same time, boosting the body's ability to clear pathogens. It functions through mechanisms quite distinct from anti-inflammatory agents, which are antagonists of specific mediators or inhibitors of specific enzymes. Plasma gelsolin functions through a pleiotropic mechanism of action, scavenging toxic actin, binding inflammatory mediators and enhancing pathogen clearance. pGSN levels decrease markedly in a variety of clinical conditions such as acute respiratory distress syndrome, sepsis, major trauma, prolonged hyperoxia, malaria, and liver injury. The strength of the correlation between magnitude of decline in pGSN and likelihood of mortality is especially striking (Lee et al, 2006; 2008; 2009; Osborn et al, 2008). Repletion of depressed plasma gelsolin levels with rhu-pGSN is expected to benefit patients through four distinct mechanisms that have been described in the literature:

1. *Sequestration of released actin from sites of damage.* This sequestration causes local depletion of pGSN while leaving large stores of pGSN continuing to circulate in healthy individuals. Modest reduction of systemic pGSN levels is then restored after healing is complete (Haddad et al, 1990; Lee et al, 1992).
2. *Prevention of the escape of mediators of inflammation from the local site.* Local depletion allows appropriate inflammation/healing to proceed while high circulating levels keep the mediators local (Bucki et al, 2000; 2005; 2008; 2010). pGSN binds and dampens pro-inflammatory mediators such as platelet-activating factor, lysophosphatidic acid, and bacterial products (Goetzel et al, 2000; Vasconcellos and Lind, 1993; Bucki et al, 2005; Bucki et al, 2008; Bucki et al, 2010; Osborn et al, 2007). pGSN can also bind fibronectin (Lind et al, 1984) and fibrin (and possibly pro-inflammatory fibrinopeptides) (Smith et al, 1987), and may 'escort' or delay binding of lysophosphatidic acid and other mediators to their receptors (Goetzel et al, 2000; Bucki et al, 2010).

3. *Enhanced uptake of gram + and gram – bacteria by tissue macrophages.* It has been shown that actin inhibits bacterial uptake and that pGSN reverses that inhibition. Excess actin in seriously ill individuals may account for immune suppression seen in these patients.

4. *Improved killing of gram + and gram – bacteria by tissue macrophages.* This function is distinct from the function that enhances bacterial uptake. It has been shown to be mediated by induction of NOS3 and is absent in NOS3 knock-out mice (Yang et al, 2015).

The development of rhu-pGSN was initiated in the 1990s and included development of the original *E. coli* cell bank and conduct of non-clinical and first clinical studies with the protein produced from culture of aliquots of this cell bank. BioAegis took over the development of rhu-pGSN, established a new *E. coli* cell line for the production of rhu-pGSN, and implemented some improvements in the manufacturing process of the therapeutic protein.

4.4. Preclinical and Clinical Experience

4.4.1. Preclinical Experience

The preclinical studies of pGSN have revealed no safety concerns related to its mechanism of action or formulation. No functional effects on the respiratory system and no systemic toxicity attributed to rhu-pGSN or the formulation excipient, 0.1% polysorbate 80 (Tween-80), were observed in these studies at the highest achievable doses. No clinically relevant pathological effects were evident in rats or monkeys following administration of pGSN or 0.1% polysorbate 80 vehicle for up to 28 days by inhalation or for 14 days by intravenous (IV) injection.

Exposures to the lower respiratory tract of rats and monkeys in the repeat-inhalation dose toxicity studies were up to approximately 75 and 250 times, respectively, the estimated level at the proposed starting dose to be administered to patients with CAP. Based upon the lack of test article-related effects, safety margins are estimated to be in excess of 4.5 and 30 times (for rat and monkey, respectively) the highest planned clinical dose.

The pharmacokinetic (PK) profile of rhu-pGSN following inhalation, intratracheal, IV, or oral administration is consistent with that of a relatively stable, high molecular weight protein. Detectable systemic absorption of rhu-pGSN following inhalation exposure is not extensive. No changes in endogenous plasma gelsolin levels were detected using an enzyme-linked immunosorbent assay (ELISA) following aerosol administration of pGSN to monkeys at presented dose levels up to 9,550 mg/kg. The half-life of rhu-pGSN-related radioactivity in the lung was approximately 10 to 16 hours in normal rats and monkeys, respectively, following pulmonary exposure.

Test article-related effects observed following repeat aerosol administration of pGSN under conditions of continuous pulmonary exposure was limited to minimal microscopic changes in the lungs of monkeys. The microscopic change is attributed to an immunogenic response as evidenced by the detection of antibodies to rhu-pGSN. The antibodies appeared to be directed against the human-specific epitopes of intact rhu-pGSN and caused no clinical or pathological signs of serum sickness. Thus, the immunogenic reaction to rhu-pGSN in monkeys appears to be a species-specific response and, therefore, is not considered to be clinically relevant.

No cardiovascular effects were noted in monkeys receiving pGSN by either inhalation or IV administration.

No eye or skin irritation was noted in rabbits after acute exposure to the product.

In summary, the preclinical profile of pGSN suggests that this drug will be well tolerated by humans and that the risk of respiratory or systemic toxicity is low.

4.4.2. Clinical Experience

Rhu-pGSN has been previously evaluated in 3 clinical studies.

Study 96-900 was a Phase 1, double-blind, randomized, controlled, within-subject, dose-escalation study in 24 healthy volunteers conducted in the United Kingdom. Patients were dosed via nebulization up to a maximum dose of 32 mg given twice per day. Adverse events (AEs) were minor and none were consistently attributed to treatment. No formation of antibodies to rhu-pGSN was observed.

Study C96-901 was a randomized, double-blind, placebo-controlled, dose-escalating, tolerability study of inhaled rhu-pGSN in 21 patients with cystic fibrosis conducted at one clinical site in Canada. Rhu-pGSN or placebo was administered via nebulization at 3.0 mg per day (Day 1 and 2), 10 mg per day (Day 3 and 4) and 25 mg per day (Day 5 to 9). Sixteen patients were randomized to rhu-pGSN and five patients to placebo (randomization ratio 3:1). Rhu-pGSN was well tolerated and no safety concerns were raised. No patients withdrew from the study. There was no negative effect on pulmonary function. There were no serious adverse events (SAEs) and no AEs were considered likely or definitely related to treatment.

Study CBC-101 was a randomized, double-blind, placebo-controlled, ascending dose, infusion trial of the PK of rhu-pGSN in patients with decreased natural gelsolin levels. This Phase 1b/2a study was conducted in Hong Kong and enrolled patients admitted to the ICU. Twenty-eight patients were enrolled; 21 patients received rhu-pGSN and 7 received placebo. The 4 cohorts were treated with ascending doses of rhu-pGSN via IV infusion according to the following scheme:

Cohort 1: Single infusion of 3 mg/kg rhu-pGSN (10 patients) or placebo (3 patients)

Cohort 2: Single infusion of 6 mg/kg rhu-pGSN (3 patients) or placebo (2 patients)

Cohort 3: Daily infusion of 6 mg/kg rhu-pGSN for 3 days (6 patients) or placebo (2 patients)

Cohort 4: Daily infusion of 6 mg/kg rhu-pGSN for 3 days (2 patients with severe multiple organ failure)

4.5. Rationale for Study and Starting Dose

The dosing for this study starts at the highest daily dose evaluated in the CBC-101 study performed in Hong Kong, followed by incrementally increased multiple doses for 3 consecutive days. The actual dose will be based on actual body weight. The placebo will be the equivalent volume on a weight basis of normal saline solution.

5. TRIAL OBJECTIVES AND ENDPOINTS

5.1. Objectives

5.1.1. Primary Objective

- To evaluate the safety and tolerability of single and multiple ascending doses of rhu-pGSN administered by once-daily IV push to hospitalized subjects with a primary admitting diagnosis of CAP
- To identify the maximum tolerated dose (MTD) or recommended Phase 2b/3 dose

5.1.2. Secondary Objectives

- To characterize the PK profile of rhu-pGSN after single or multiple IV doses

5.1.3. Exploratory Objectives

- To assess the quantitative relationship of pGSN levels at baseline with clinical outcomes, changes in prognostic indices and inflammatory biomarkers, and etiologic pathogen type
- To assess the relationship between rhu-pGSN dose and clinical response and changes in surrogate biomarkers of efficacy

5.1.4. Immunogenicity Objective

- To investigate the post-treatment development of antibodies against rhu-pGSN by Day 28

5.2. Endpoints

5.2.1. Primary Endpoint

- Incidence, causality, and severity of AEs and SAEs graded according to the National Cancer Institute (NCI) Common Terminology Criteria for Adverse Events (CTCAE) version 4.03 (or equivalent), clinically significant laboratory and/or electrocardiogram (EKG) abnormalities, death irrespective of cause, cause of death per investigator, including relationship to study drug; use of vasopressors, intubation, or transfer to the ICU or equivalent through Day 7

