5.2.2. Secondary Endpoints

- PK for rhu-pGSN including, but not limited to maximum concentration (C_{max}), time to maximum concentration (T_{max}), terminal half-life ($T_{1/2}$), area under the curve from time zero to 8 hours (AUC_{0-8}), area under the curve from time zero to infinity (AUC_{inf}) (levels measured within 30 minutes predose, 5-10 minutes after the end of administration, and 2, 8, 12 and/or 16, and 24 hours (\pm 30 minutes) after each dose (Day 3 sampling in multiple-dose arms is optional)

- Incidence, causality, and severity of AEs and SAEs graded according to the NCI CTCAE version 4.03 (or equivalent); clinically significant laboratory and/or EKG abnormalities as required by SOC; death irrespective of cause; cause of death per investigator, including relationship to study drug; use of vasopressors, intubation, or transfer to the ICU or equivalent through Day 28 (secondary time point)

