9.2.6. Laboratory Assessments

All routine clinical laboratory assessments will be performed by the hospital laboratory or equivalent, when appropriate. Where indicated, handling and shipping clinical laboratory samples to a central laboratory will be outlined in the Laboratory Manual.

Screening laboratory and other tests can serve as baseline values for participants (no need to repeat lab tests at entry if done within the prior 36 hours unless dictated by SOC).

The laboratory evaluations will include:

1. Hematology: complete blood count with differential white count and reticulocyte count, and platelet count; PT/PTT
2. Comprehensive metabolic profile (including chemistries/electrolytes, TP/albumin, BUN/creatinine, C-reactive protein (CRP), lactose dehydrogenase (LDH), creatine phosphokinase (CPK), alanine aminotransferase (ALT), aspartate aminotransferase (AST), total bilirubin, alkaline phosphatase, and amylase or lipase)
3. Respiratory function (oxygen saturation by pulse oximetry; arterial blood gas tests only at the caregiver's discretion)

Abnormal laboratory test results considered clinically significant by the Investigator or that require treatment should be reported as AEs in the eCRF.

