10.6. Laboratory Abnormalities

To the extent possible, all laboratory abnormalities observed during the course of the study will be included under a reported AE term describing a clinical syndrome (e.g., elevated BUN and creatinine in the setting of an AE of "renal failure"). In these cases (e.g., an AE of renal failure), the laboratory abnormality itself (e.g., elevated creatinine) does not need to be recorded as an AE.

If a laboratory abnormality cannot be reported as a clinical syndrome, AND if the laboratory abnormality results in a therapeutic intervention (i.e., concomitant medication or therapy), is a DLT, or is judged by the Investigator to be of other clinical relevance, then the laboratory abnormality should be reported as an AE.

Subjects experiencing AEs or clinically significant laboratory abnormalities will be assessed and appropriate evaluations performed until all parameters have returned to baseline levels or are consistent with the subject's then-current physical condition.

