11.4. Criteria for Evaluation and Statistical Methods

11.4.1. Safety

AE data will be summarized by counts and proportions of subjects having an AE, each AE type, and an AE of each System Organ Class. These summaries will be provided for each dose and placebo (all placebo subjects combined). Serious AEs will be summarized similarly. Reasons for any early discontinuations will be summarized similarly.

Laboratory data in relation to normal range values will be summarized via counts and percentages of subjects below, within, and above the respective normal range, and by summary statistics (N, mean, median, standard deviation, minimum, maximum, 90% confidence intervals, etc.) for baseline, each observed time point, and change from baseline at each observed time point for continuous lab endpoints.

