### **11.2.2 Biostatistical Methods**

All laboratory data collected at scheduled and unscheduled visits will be included in the listings, but only results collected as scheduled visits will be included in the summary tables.

Results for individual parameters may be reported in different units depending on the analyzing laboratory. If required, the results (and the corresponding normal range cut-off values) for individual parameters may be converted to International System of Units (S.I.) units to summarize the data.

For the all parameters where a unit value has been reported, the parameter names that will be used in the outputs will comprise of the test name and the unit of measure, for example, 'Albumin (g/L)'. Parameters will be sorted alphabetically within tables and listings.

For all parameters where a normal range limit value is reported, the normal range will be derived based on the available lower and upper limit values and any reported mathematical symbols. If both a lower and upper limit value is available, the normal range will be presented as '(Lower, Upper)'.

The reported results for each parameter with a defined normal range will be classified ('Low', 'Normal', 'High') in relation to the defined normal range limits. If a result is equal to the normal range cut-off value, the result will be considered 'Normal'.

The change from baseline values at each post-baseline visit will be calculated for all parameters with continuous results (except for specific gravity and pH).

The decimal precision for each parameter will be based on the maximum number of decimals to which the reported result or the normal range limits are presented to in the raw data. The results and normal ranges will be displayed to the same decimal precision in the listings.

If a result for a parameter that is normally considered continuous is reported as a range (i.e., the result for basophils is reported as '<0.01' for a single time point), the result may be converted to a numeric value that is smaller than the reported result to contribute to the derivations and the summary statistics. Any conversion rules that are applied will be highlighted in the footnotes of the affected tables and listings. The original reported result value will however be included in the listing.

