The laboratory result tables will present summary statistics for each laboratory parameter within the specific test panel. For each parameter, summaries will be presented for the baseline and each scheduled post-baseline visit. In addition, summaries will be presented for the change from baseline values at each scheduled post-baseline visit.

Additionally, counts (%) of number subjects with values out of normal range at each scheduled time point will also be presented along with shift tables that will represent the changes in normal range categories across post-baseline time points.

The listings of laboratory parameters will include all the information (fields) collected. In addition, the observations that are used as the baseline record (value) for each parameter will be flagged, and the change from baseline values at each post-baseline visit will be presented.

For all parameters, standardized values will be reported.

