**Programming Note:**  
Repeat Listing 16.2.7.4.1 for MAD.

Listing 16.2.8.1.1.1.1 SD: CBC  
 Protocol: BTI-201  
 Intent-to-Treat Population  
 Cohort 1: rhu-pGSN 6 mg/kg

Subject	Parameter (Unit)	Study Visit	Sample Date/ Time		Actual Value	Change from Baseline 	Reference Ranges	High/ Low Flag	Clinical Significance	Abnormality Description
			(DDMMYYYY/ HH:MM)	(DDMMYYYY/ HH:MM)						
XXX	Haemoglobin (unit)	Screening	DDMMYYYY/ HH:MM	DDMMYYYY/ HH:MM	xx	xx, xx				
		Day 1 	DDMMYYYY/ HH:MM	DDMMYYYY/ HH:MM	xx	xx, xx				
		Day 2	DDMMYYYY/ HH:MM	DDMMYYYY/ HH:MM	xx	xx, xx	H	NCS		
		Day 3 or 4	DDMMYYYY/ HH:MM	DDMMYYYY/ HH:MM	xx	xx, xx	L	CS		XXXXXXXXXXXXXXXXXX

Etc. Etc.

Note: Baseline. Baseline is defined as the last valid, non-missing assessment prior to first study drug administration.  
 L = Below Normal Range, H = Above Normal Range, NCS = Not Clinically Significant, CS = Clinically Significant.

Clinical cut-off date: DDMMYYYY

Program: filepath\_name, Output: filepath\_name (version x.x) Created: DDMMYYYY HH:MM

Programming Note:  
 Include all time points and all parameters.

Listing 16.2.8.1.1.2 MAD: CBC

Protocol: BTI-201

Intent-to-Treat Population

Cohort 2: rhu-pGSN 6 mg/kg

Programming Note:  
Repeat Listing 16.2.8.1.1.1 for MAD.  
Include all time points and all parameters.

Listing 16.2.8.1.2.1 SD: Abnormal CBC  
 Protocol: BTI-201  
 Intent-to-Treat Population  
 Cohort 1: rhu-pGSN 6 mg/kg

Subject	Parameter (Unit)	Study Visit	Sample Date/ Time		Actual Value	Change from Baseline 	Reference Ranges	High/ Low Flag	Clinical Significance	Abnormality Description
			(DDMMYYYY/ HH:MM)	(DDMMYYYY/ HH:MM)						
XXX	Haemoglobin (unit)	Day 2	DDMMYYYY/ HH:MM	DDMMYYYY/ HH:MM	xx	xx	xx, xx	H	NCS	
		Day 3 or 4	DDMMYYYY/ HH:MM	DDMMYYYY/ HH:MM	xx	xx	xx, xx	L	CS	XXXXXXXXXXXXXXXXXXXX
Etc.	Etc.									

Note: Baseline. Baseline is defined as the last valid, non-missing assessment prior to first study drug administration.  
 L = Below Normal Range, H = Above Normal Range, NCS = Not Clinically Significant, CS = Clinically Significant.

Clinical cut-off date: DDMMYYYY

Program: filepath\_name, Output: filepath\_name (version x.x) Created: DDMMYYYY HH:MM

Programming Note:  
 Include all time points and all parameters.

Listing 16.2.8.1.1.2.2 MAD: Abnormal CBC

Protocol: BTI-201

Intent-to-Treat Population

Cohort 2: rhu-pGSN 6 mg/kg

Programming Note:  
Repeat Listing 16.2.8.1.2.1 for MAD.  

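### Clinically significant laboratory abnormalities are part of the primary endpoint, but no planned laboratory table counts the subjects who have one

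*Protocol*

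**What the plan says.** Protocol 5.2.1 lists, among the components of the primary endpoint through Day 7, "clinically significant laboratory and/or electrocardiogram (EKG) abnormalities, death irrespective of cause". Protocol 5.2.2 repeats the list through Day 28 and labels this a secondary time point, but there the component reads "clinically significant laboratory and/or EKG abnormalities as required by SOC". The synopsis carries the same two wordings.

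On recording, Protocol 9.2.6 states: "Abnormal laboratory test results considered clinically significant by the Investigator or that require treatment should be reported as AEs in the eCRF". Protocol 10.6 asks that laboratory abnormalities be placed under a clinical syndrome term where possible, in which case "the laboratory abnormality itself (e.g., elevated creatinine) does not need to be recorded as an AE". An abnormality that fits no syndrome is reported as an AE if it leads to intervention, is a DLT, or the investigator considers it otherwise relevant.

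On analysis, Protocol 11.4.1 plans "counts and percentages of subjects below, within, and above the respective normal range", plus summary statistics. SAP 11.2.2 follows this. Results "will be classified ('Low', 'Normal', 'High') in relation to the defined normal range limits", and "counts (%) of number subjects with values out of normal range at each scheduled time point will also be presented", together with shift tables. Only results from scheduled visits enter the summary tables; unscheduled results are listed. The laboratory listing shells (16.2.8 series) have a clinical significance column with the key "NCS = Not Clinically Significant, CS = Clinically Significant".

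**The concern.** A primary safety endpoint should lead to a planned number for each of its named components. Here the component is the clinically significant result, which is an investigator's judgement, while the planned laboratory tables rest on the reference range. These are different quantities. A value can be out of range and unimportant, and an important result from an unscheduled draw never reaches a summary table.

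The study is meant to support dose escalation and the choice of a dose for later trials. If the laboratory component is only listed, a reader of the tables cannot compare its frequency across 6, 12 and 24 mg/kg and placebo, either through Day 7 as the primary endpoint requires or through Day 28. The Day 28 wording adds a second difficulty. Two time points described as one endpoint should use one definition, and the standard-of-care qualifier makes them differ.

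**Working it through.** The plan states no figure for this component, so the check is an audit of endpoint against output.

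**1. Laboratory tables.** SAP Section 17 lists three panels (CBC, coagulation, comprehensive metabolic profile), each with one table of actual and change values and one shift table, for SD and for MAD: 3 × 2 × 2 = 12 tables (14.3.4.1 to 14.3.4.3). The shells show summary statistics or Low/Normal/High by baseline category, per parameter and visit. Tables with a CS category: 0 of 12. Tables giving a per-subject count through Day 7 or through Day 28: 0 of 12.

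**2. Where the CS rating does appear.** SAP Section 18 lists, for the same panels, one full and one abnormal-only listing each, for SD and MAD: 3 × 2 × 2 = 12 listings. The shells show the clinical significance column. SAP Section 3 says that all eCRF data go into the listings, so I take the flag to be a collected field.

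**3. Comparison with other safety data.** SAP 11.3.2 and 11.4.2 tabulate Normal, Abnormal NCS and Abnormal CS for vital signs (Tables 14.3.4.5.1 and 14.3.4.5.2) and EKG (14.3.4.7.1 and 14.3.4.7.2). The laboratory data lack the equivalent. The EKG shells show only baseline and Day 28/early termination.

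**4. Can the AE tables stand in?** Under 9.2.6 a CS result becomes an AE. Under 10.6 it may be absorbed into a syndrome term, and the table then shows the syndrome without saying whether a laboratory result lay behind it. SAP 11.1.2 plans TEAE summaries by SOC and preferred term, seriousness, death, severity, causality and discontinuation. None is cut at Day 7. The AE route therefore captures the events but does not give the count.

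**5. Day 7 against Day 28.**

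| | Protocol 5.2.1 | Protocol 5.2.2 |
|---|---|---|
| Window | through Day 7 | through Day 28 |
| Qualifier | none | tied to standard of care |

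Protocol Tables 5 and 6 schedule CBC, coagulation and metabolic tests at Days 14 and 28, and an EKG at the Day 28 visit, for every subject. Taken literally, the qualifier leaves those results out unless standard of care also called for them. SAP 11.2.2 and 11.4.2 apply no such filter, so the mismatch lies in the endpoint text and not in the planned output.

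**6. Scale.** Each dose cohort has 6 active and 2 placebo subjects. One subject is 1/6 = 16.7% of an active group, so whether a single CS result is counted changes the displayed rate noticeably.

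**The case against.** The strongest reply has four parts.

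- **The SAP has not drifted from the protocol.** Protocol 11.4.1 itself plans range categories, and SAP 11.2.2 carries that out. This is correct. The gap begins in the protocol, between its endpoint section and its statistics section, and the SAP inherits it.
- **The events are not lost.** Under 9.2.6 and 10.6 a CS result is either reported as an AE or sits inside a reported syndrome, and so enters the TEAE tables by dose and placebo. This largely stands. What is missing is a separate laboratory count, and any cut at Day 7.
- **The listings suffice for 32 subjects.** The abnormal-value listings carry the flag by cohort, so a reader could count by hand. That is possible, but a hand count from listings is not a planned estimate of a primary endpoint component, and the time windows would be the reader's own choice.
- **The range-based tables are informative.** They are per parameter and per visit, cross-classified by baseline category, and stand beside change from baseline. A reader might infer that out-of-range counts saturate in acutely ill patients and cannot show a dose-related signal. The documents do not support that: no any-test-abnormal rate is planned, and parameter-level shifts could show a signal.

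**Conclusion.** The point holds for laboratory results. A named component of the primary endpoint, the investigator-rated CS laboratory abnormality through Day 7, has no table of its own by dose or placebo (0 of 12 laboratory tables), and the TEAE tables recover it only in part. The different Day 28 wording is a smaller, separate defect of text. Both should be corrected, but neither threatens the safety data themselves, which are collected and listed.

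Three stronger readings are tempting and should not be drawn:

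- A reader might infer that the component has three competing definitions. It has one investigator-judged term, one added qualifier in a secondary endpoint, and one missing table. The SAP does not redefine clinical significance; it summarises something else.
- A reader might infer that no CS result of any kind is tabulated. EKG and vital signs interpretations are.
- A reader might infer that the reported Day 28 rate could fall below the Day 7 rate. No planned output applies the standard-of-care filter, and the documents give no rates from which to size such an effect.

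The conclusion assumes that the SAP's table index is complete and that the CS column in the listing shells reflects a collected field.

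**What to change.** 1. In Protocol 5.2.2 and the matching synopsis entry, delete *as required by SOC*, so that Day 7 and Day 28 use one definition.
2. Add one SAP table, in SD and MAD versions: n (%) of subjects with at least one post-dose laboratory result flagged CS, from scheduled or unscheduled testing, overall and by panel, through Day 7 and through Day 28, by dose and placebo. State the date rule for each cut, since unscheduled results have no visit label.
3. State in Protocol 10.6 or SAP 11.2.2 that a result absorbed into a syndrome AE still counts in this table.
4. Keep the range and shift tables as supportive output.

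The cost is a few words in the protocol and one table built from a flag already planned for the listings. The main downside is that the flag is an investigator's judgement and may vary between sites, which is why the range-based tables should stay beside it. Some patients may also have CS values before dosing, so a row for subjects not flagged CS at baseline would help interpretation.
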